## 1. Protocol Summary

### 1.1. Synopsis

*Structure:* Single-center, prospective, randomized, parallel-group, open-label, controlled study

*Duration:* 30 to 60 days

*Study Intervention Groups:* Intranasal Tear Neurostimulator (ITN) [TrueTear®]

*Control:* ITN device applied extranasally

*Dosage/Dose Regimen:* Single intranasal or extranasal application of the ITN for approximately 3 minutes

*Randomization/Stratification:* Randomization (2:1) to either intranasal or extranasal application of the ITN

*Visit Schedule:* This study consists of 2 visits, a Screening Visit and a randomized Application Visit/study exit (Day 0), separated by up to 60 days.

[figure not shown]
### 1.2. Schema

The study schema is provided in [Figure 1-1](#).

**Figure 1-1 Study Schema**

Visit 1 (Day -60 to Day -30)  
Screening / Study Enrollment

Visit 2 (Day 0)  
Randomized Application / Study Exit

Protocol 1919-802-019

[REDACTED]  
Intranasal Tear Neurostimulator

[figure not shown]
### 1.3. Schedule of Activities

[REDACTED]

[figure not shown]
CONFIDENTIAL

Protocol 1919-802-019

Protocol 1919-802-019

Intranasal Tear Neurostimulator

## 2. Introduction

The Intranasal Tear Neurostimulator (ITN; TrueTear®), was granted a de novo petition by the US FDA on May 17, 2018 ( [REDACTED] ) with the following indications for use:

- The TrueTear ITN provides a temporary increase in tear production during neurostimulation to improve dry eye symptoms in adult patients with severe dry eye symptoms.

### 2.1. Study Rationale

The ITN delivers small electrical currents to the nasal cavity, stimulating the anterior ethmoidal branch of the trigeminal nerve, leading to activation of the nasolacrimal reflex pathway responsible for basal and bolus tear production. Numerous studies have been conducted to demonstrate that tear production is significantly increased during application of the ITN.

Tears are a complex aqueous fluid composed of proteins, lipids, and mucins. As the chemical composition of tears is essential for their optimized function, it was of interest to determine whether or not tears produced during application of the ITN were diluted (ie, reflex tears). Studies conducted to date have demonstrated equivalent lipid and protein concentrations in tears collected immediately following application of the ITN compared to baseline. In addition, mucin secretion stimulated by application of the ITN was suggested in a pilot study (OCUN-003). Specifically, a significantly higher ratio of degranulated to non-degranulated conjunctival goblet cells post-ITN stimulation was found, suggestive of mucin release.

This study aims to build on the data collected in the pilot study (OCUN-003) to verify that mucin secretion from goblet cells is stimulated with application of the ITN. These data would further support the conclusion that the tears stimulated with application of the ITN are representative of a complete basal tear as opposed to a diluted reflex fluid.

### 2.2. Background

DED is defined as a multifactorial disorder of the ocular surface characterized by loss of tear film homeostasis and ocular symptoms, in which tear film instability and hyperosmolarity, ocular surface inflammation and damage, and neurosensory abnormalities play etiological roles (Craig 2017). An estimated 25 million Americans are reported to have DED, making DED one of the most common reasons patients seek care with their eye care professional (Behrens 2006, DEWS 2007).

Signs of dry eye include ocular surface damage, reduced tear volume, delayed tear clearance, abnormal tear osmolarity and decreased tear film break-up time. Accompanying symptoms can include dryness, grittiness, burning, stinging, discomfort, photophobia and blurry or fluctuating vision. These symptoms are typically worse later in the day and can be triggered or exacerbated by environmental conditions such as low humidity or wind.

## Intranasal Tear Neurostimulator

While progress continues to further our understanding of the underlying pathology of DED and corresponding potential targets for treatment intervention, to date treatment of DED remains a large unmet medical need ([Bielory 2016](#), [Wolffsohn 2017](#)).

Neuromodulation represents a therapeutic strategy for directly stimulating peripheral neuronal connections to attenuate neuronal dysfunction and alleviate symptoms in treating DED. The ITN acts via stimulation of the nasociliary nerve (peripheral branch of the trigeminal nerve), activating the nasolacrimal reflex through a parallel pathway, acting directly on multiple components of the LFU such as lacrimal glands, goblet cells, and meibomian glands ([LeDoux 2001](#), [Dartt 2009](#), [Bron 2017](#)). Therefore, not only is aqueous production stimulated, but also secretion of protein, mucin, and meibum.

It was recently demonstrated that application of the ITN can trigger both an increase in tear volume and goblet cell degranulation in patients with DED ([Gumus 2017](#)). Moreover, Dieckmann et al demonstrated a significant reduction in the area and size of goblet cells immediately after stimulation with ITN, suggesting an increase in mucin secretion ([Dieckmann 2017](#)). Data reported by [Green 2017](#) and [Woodward 2017](#) have concluded that protein and lipid concentration of tears collected post-application of the ITN is equivalent to that of tears collected pre-stimulation, suggesting that the ITN promotes release of proteins from secretory granules in the lacrimal gland and meibum (lipid) from Meibomian glands. Lastly, [Pondelis 2017](#) demonstrated a decrease in the area and perimeter of meibomian glands immediately after 3-minute application of the ITN, reinforcing the suggestion that the ITN can stimulate lipid secretion. These studies to date demonstrate a clear effect of neurostimulation with ITN on all major components of tear film, thus offering a promising new approach for treatment of DED.

[figure not shown]
### 2.2.1. Device Description

The ITN is a non-surgical device intended for the application of low level electrical stimulation to sensory neurons of the nasal cavities to increase tear production and improve dry eye symptoms.

The device consists of four distinct non-sterile subassemblies, as listed below and shown in [Figure 2-1](#):

1. A reusable base unit which produces the electrical stimulation waveform.
2. A disposable tip that provides the contact surface for the stimulation to the intranasal skin and mucosa.
3. A reusable charger which recharges the sealed battery inside the base unit.
4. A reusable cover to protect the disposable tip.

## Intranasal Tear Neurostimulator

[figure not shown]
**Figure 2-1** Intranasal Tear Neurostimulator System Components

Base unit + disposable tip

Cover

[figure not shown]
Charger

Figure 2-2 shows the correct application of the device.

**Figure 2-2** Correct Application of the Intranasal Tear Neurostimulator

### Intranasal Tear Neurostimulator

the material used in contact lenses) that contacts the inside of the nose to provide stimulation. Each tip may be used up to 48 hours. After 48 hours, the used tip should be discarded and a fresh tip should be attached. A separate cover can be used to protect the tip and base unit when the device is not in use.

### 2.2.2. Extranasal Control Description

The comparator arm in this study is an identical, active ITN device which will be applied extranasally as shown in [Figure 2-3](#). Participants will be instructed to place the tips of the device on the tip of the nose, hydrogel side down.

**Figure 2-3** Schematic Showing Location of Tips for Extranasal Control Application

### 2.3. Benefit/Risk Assessment

The treatment of DED remains a large unmet medical need. Patients with DED generally present with ocular surface epithelial damage attributed to either or both inadequate tear production and tear film instability. These pathophysiological changes are generally accompanied by patient reported symptoms of ocular surface discomfort, often described as dryness, burning, pain, grittiness; and blurred vision.

Protocol 1919-802-019

#### Intranasal Tear Neurostimulator

The benefit of the ITN is the replenishment of endogenous tears leading to subsequent improvement in ocular surface health and dry eye symptoms, thus providing a valuable treatment option for patients with DED.

To date, application of the ITN is safe and well-tolerated and there were no unexpected safety concerns. No SAEs have been observed. The most frequently reported ADEs were all related to nasal findings consisting of: nasal pain/discomfort (reported as aching, burning, discomfort, pain, or soreness), transient intranasal electrical discomfort, nosebleed, and nasal congestion.

[REDACTED]  
Intranasal Tear Neurostimulator

### 3. Objectives and Endpoints

Objectives	Endpoints

Primary:
 
To evaluate the change in goblet cell degranulation following randomized application of device
 

• Immunofluorescence staining of cells obtained via impression cytology

 
[REDACTED]
	

• Mean change in goblet cell degranulation post-intranasal application of the ITN at the Application Visit compared to without-intranasal application of the ITN at the Screening Visit.

[REDACTED]

Intranasal Tear Neurostimulator

## 4. Study Design

### 4.1. Overall Design

This is a prospective, randomized, controlled, parallel-group, open-label, single-center study in participants with DED.

This study consists of 2 visits: Screening and the Application Visit (Day 0). A study schema is located in Section 1.2 and the Schedule of Visits and Procedures is located in Section 1.3.

Participants will be randomized (in a 2:1 ratio) at Screening to either intranasal or extranasal acute (single) application of the ITN, which they will apply accordingly for approximately 3 minutes during the Application Visit. Approximately 36 participants with DED will be enrolled at a single site in the United States.

At Screening, and prior to any testing, participants will be provided with an IRB-approved ICF which they will have the opportunity to review and ask questions about before written consent is obtained. The Screening Visit should occur 30 to 60 days prior to the Application Visit.

The Application Visit will be separated into pre-ITN application and post-ITN application assessments. CDVA, slit-lamp examination, TMH measurement via OCT, and tear collection will occur at least 45-minutes prior to ITN application, and will be performed again following ITN application. Impression cytology will be performed following these procedures after ITN application.

Safety measures will be assessed before and after ITN application at the Application Visit, including CDVA and slit-lamp biomicroscopy. AEs will be queried prior to study exit.

#### 4.1.1. Clinical Hypotheses

Post-application of the ITN, a greater percentage of goblet cells will be degranulated relative to pre-application of the ITN as measured by immunofluorescence staining of cells collected by impression cytology.

### 4.2. Scientific Rationale for Study Design

The ITN stimulates the anterior ethmoidal branch of the trigeminal nerve in the upper nasal cavity, leading to an increase in tear production with concomitant increases in proteins and lipids. In addition, evidence suggests degranulation of conjunctival goblet cells occurs post-application of the ITN.

Data from Study OCUN-014 demonstrated that tear film protein and lipid concentrations post-ITN application were equivalent to those collected prior to ITN application. In a pilot study (OCUN-003), participants with DED were assigned to both intranasal and extranasal application of the ITN for 3 minutes in random sequence. Results suggested that goblet cell degranulation post-intranasal application of the ITN was greater than prior to intranasal application, and that intranasal application demonstrated significantly greater goblet cell degranulation relative to

### Intranasal Tear Neurostimulator

extranasal application. In both OCUN-003 and OCUN-014, ITN application demonstrated a statistically significant increase in tear production as measured by TMH. While these and other studies have provided support for the ITN's putative mechanisms of action, the effect of stimulation on ocular surface pro-inflammatory cytokines has not been clearly established.

The rationale for this study is to confirm the ITN's effect on goblet cell release of mucin and to explore its effect on tear film cytokine concentration.

#### **4.3. Justification for Treatment Administration**

The ITN will be applied in accordance with the instructions for use.

#### **4.4. End of Study Definition**

The end of study is defined as the date of the Application Visit for the last participant in the study, or the AE query on this day for the last participant in the study.

A participant is considered to have completed the study if he/she has completed both the Screening Visit and Application Visit or exited early from the study.

[REDACTED]  
Intranasal Tear Neurostimulator

## 5. Study Population

The study population will consist of adult male and female participants with objective and subjective evidence of DED. The study will be conducted at a single site and will enroll up to 36 participants who have provided written informed consent and have met the eligibility criteria below.

Prospective approval of protocol deviations to recruitment and enrollment criteria, also known as protocol waivers or exemptions, is not permitted.

### 5.1. Inclusion Criteria

Participants are eligible to be included in the study only if all of the following criteria apply:

1.	Age
1.01	Participants must be at least 22 years of age, at the time of signing informed consent
3.	Sex
3.01	Male and female
4.	Informed Consent
4.01	Capable of giving verbal and signed informed consent, which includes compliance with the requirements and restrictions listed in the ICF and in this protocol
4.02	Written informed consent from the participant or legally authorized representative has been obtained prior to any study-related procedures
4.03	Written documentation has been obtained in accordance with the relevant country and local privacy requirements, where applicable. (eg, Written Authorization for Use and Release of Health and Research Study Information for the United States)
5.	Other

## Intranasal Tear Neurostimulator

[figure not shown]
[figure not shown]
5.01	Have not worn contact lenses for at least 7 days prior to the Screening Visit and are willing to forego the use of contact lenses for the duration of the study
5.02	The participants should be literate, able to speak English, and able to complete questionnaires independently

**5.2. Exclusion Criteria**

Participants are excluded from the study if any of the following criteria apply:

[figure not shown]
[figure not shown]
1.	Medical Conditions
1.01	Have chronic or recurrent epistaxis, coagulation disorders, or other conditions that, in the opinion of the investigator, may lead to clinically significant risk of increased bleeding
1.02	Have had nasal or sinus surgery (including history of application of nasal cauter) or significant trauma to these areas
1.04	Have had a corneal transplant in either or both eyes
1.06	Have a cardiac demand pacemaker, implanted defibrillator, or other active implanted metallic or active implanted electronic device in the head
1.07	Have a systemic condition or disease not stabilized or judged by the investigator to be incompatible with participation in the study
2.	Prior/Concomitant Therapy

## Intranasal Tear Neurostimulator

	
2.02	Have used contact lenses within 7 days prior to the Screening Visit or anticipate the use of contact lenses at any time during the duration of the study
	
3.	Prior/Concurrent Clinical Study Experience
3.01	Current enrollment in an investigational drug or device study or participation in such a study within 30 days of entry into this study
	

Intranasal Tear Neurostimulator

	
5.	Other
5.01	Females who are pregnant, nursing an infant, or planning a pregnancy during the study. WOCBP who do not agree to use a reliable form of contraception throughout the study.
	

### **5.3. Lifestyle Considerations**

No lifestyle consideration restrictions are required.

### **5.4. Screen Failures**

Screen failures are defined as participants who consent to participate in the clinical study but are not subsequently entered in the study. A minimal set of screen failure information is required to ensure transparent reporting of screen failure participants to meet the Consolidated Standards of Reporting Trials publishing requirements and to respond to queries from regulatory authorities. Minimal information includes demography, screen failure details, eligibility criteria, and any SAE.

[REDACTED]  
Intranasal Tear Neurostimulator

## 6. Study Intervention

Study intervention is defined as any investigational intervention(s), marketed product(s), placebo(s), or medical device(s) intended to be administered to a study participant according to the study protocol.

### 6.1. Study Interventions Administered

Study Intervention	TrueTear Intranasal Tear Neurostimulator (ITN) – Intranasal Application	TrueTear Intranasal Tear Neurostimulator (ITN) – Extranasal Application (Control)
Number and Timing of Interventions	Single application at Application Visit	Single application at Application Visit
Manufacturer	Allergan	Allergan

#### 6.1.1. Instructions for Use and Administration

##### Intranasal Application

At the Application Visit, participants will be trained on the application of the ITN based on approved instructions for use and instructed to administer a single stimulation for approximately 3 minutes. A sponsor representative may be present for training purposes.

[REDACTED]

### 6.2. Preparation/Handling/Storage/Accountability

[REDACTED]

Intranasal Tear Neurostimulator

### **6.3. Measures to Minimize Bias: Randomization and Blinding**

At the time of randomization at the Screening Visit, qualified participants will be randomly assigned in a 2:1 ratio to receive either intranasal ITN or extranasal (control) ITN stimulation at the Application Visit. Electronic randomization methods will be used to create a randomization scheme prior to study start.

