## Intranasal Tear Neurostimulator

**Table 8–1** Effectiveness Assessments

Assessment	Timing	Measurement
Goblet cell degranulation	

• Screening Visit

• Application Visit after randomized ITN application

	Impression cytology followed by immunofluorescence staining

[figure not shown]
Intranasal Tear Neurostimulator

A large black rectangular box redacting the majority of the page content.

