## 9.2. Sample Size Determination

Approximately 36 participants are required to apply randomized device and complete the Application Visit, in which 24 participants will be in the intranasal ITN application group and 12 will be in the extranasal ITN application group. Approximately 50 participants may be enrolled to meet this goal.

It is assumed that the standard deviation of the change in goblet cell degranulation post-ITN application versus pre-ITN application is 4.52. With 24 participants in the intranasal ITN application group, it is estimated that the accuracy of a half width of the 95% CI is approximately 1.8.

Intranasal Tear Neurostimulator

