##### **9.4.1.1. Primary Effectiveness Endpoint**

- The mean change in goblet cell degranulation post-intranasal application of the ITN at the Application Visit compared to without-intranasal application of the ITN at the Screening Visit.

Intranasal Tear Neurostimulator

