#### **9.4.1.3. Primary Effectiveness Analyses**

The primary effectiveness variable will be the number of goblet cells degranulated in the study eye. The study eye will be the eye with the lower tear meniscus height prior to the application or, if both eyes are equal, the right eye.

The primary effectiveness endpoint will be the mean change in goblet cell degranulation post-intranasal application of the ITN at the Application Visit compared to without-intranasal application of the ITN at the Screening Visit. Summary statistics of count, mean, median, minimum, and maximum will be provided to evaluate the change in the number of degranulated goblet cells and a 95% CI will also be provided.

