## Intranasal Tear Neurostimulator

Parameter Group	Parameter	Value
Treatments	Investigational Therapy or Treatment	Intranasal Tear Neurostimulator (ITN)
	Intervention Type	Device
	Pharmacological Class of Invest. Therapy	N/A
	Dose per Administration	3 minutes
	Dose Units	N/A
	Dosing Frequency	Once
	Route of Administration	Intranasal application of ITN
	Current Therapy or Treatment	No
	Added on to Existing Treatments	No
	Control Type	Extranasal application of ITN
	Comparative Treatment Name	ITN
Trial design	Study Type	Interventional
	Intervention Model	Parallel
	Planned Number of Arms	2
	Trial is Randomized	Yes
	Randomization Quotient	2:1 (intranasal to extranasal)
	Trial Blinding Schema	Open-label
	Stratification Factors	N/A
	Adaptive Design	No
	Study Stop Rules	None

Intranasal Tear Neurostimulator

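### Section 6.3 sets randomization but states no masking of the slide reader, although the primary result is a before/after cell count within one arm of an open-label trial

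*Protocol*

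**What the plan says.** Section 4.1 declares the design: "This is a prospective, randomized, controlled, parallel-group, open-label, single-center study in participants with DED". The synopsis says the same, and the Appendix 5 tabular summary gives open-label as the value for "Trial Blinding Schema".

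Section 6.3 is the section on bias control, and its heading is "Measures to Minimize Bias: Randomization and Blinding". Apart from stating the 2:1 allocation at Screening, its only provision is "Electronic randomization methods will be used to create a randomization scheme prior to study start". Despite its heading, it says nothing about masking the participant, site, laboratory or slide reader. No redaction is marked inside it.

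Section 9.4.1.3 defines the outcome: "The primary effectiveness variable will be the number of goblet cells degranulated in the study eye". Table 8-1 gives the method as "Impression cytology followed by immunofluorescence staining", done at Screening and again after device application at the Application Visit. The contrast in Section 9.4.1.1 begins "The mean change in goblet cell degranulation post-intranasal application of the ITN at the Application Visit compared to without-intranasal application of the ITN at the" and closes by naming Screening as the reference. Section 4.1.1 states the expected direction in advance: a larger share of degranulated cells after application than before.

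Some text cannot be seen. The Schedule of Activities (1.3) is redacted, Sections 8.1 and 8.2 show only headings, and most of the page after Table 8-1 is blacked out.

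**The concern.** Open-label application is unavoidable here, because the participant knows where the device is placed. Open-label slide reading can be avoided.

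The primary estimate is a difference between two slides from the same person, with the expected direction known. A reader who sees the visit or the date knows which slide is supposed to show more degranulation, even without knowing the arm. A tendency to score the later slide higher goes straight into the primary estimate, and pairing does not cancel it because it acts on one member of the pair.

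The extranasal arm could in principle absorb a shift that depends on visit alone, since it would affect both arms alike. The planned primary result does not subtract that arm, so the protection is not used. It follows that masking to arm alone would not protect the primary result. Masking to visit is the essential part.

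**Working it through.** **Inputs from the protocol**
- SD of the change: 4.52. Section 9.2: "It is assumed that the standard deviation of the change in goblet cell degranulation post-ITN application versus pre-ITN application is 4.52".
- Intranasal arm: n = 24 (Section 9.2).
- Planned precision: 95% CI half-width of approximately 1.8 (Section 9.2).

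**Assumed inputs**
- Reader shift b on Application Visit slides: 0.5, 1 or 2 cells. The protocol gives no figure for this.
- The SD is taken to be in cells, to match the outcome in Section 9.4.1.3.
- A positive finding means that the 95% CI lies wholly above 0. The protocol states hypotheses in Section 9.1 but plans only summary statistics and a CI, so this decision rule is added for the illustration.

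**Step 1: reproduce the protocol's figure**

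SE = 4.52 / √24 = 0.923.

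Half-width with the normal quantile = 1.960 × 0.923 = 1.81, which agrees with the stated 1.8. With the t quantile on 23 degrees of freedom it is 2.069 × 0.923 = 1.91.

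**Step 2: carry a reader shift through**

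Observed change = true change + b + random error, so the expected estimate is the true change plus b. With a true change of 0, the chance that the CI lies above 0 is P(T > 2.069), where T is noncentral t with 23 degrees of freedom and noncentrality b / SE.

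| Assumed shift b (cells) | b / SD | b / SE | Chance CI lies above 0 |
|---|---|---|---|
| 0 | 0 | 0 | 2.5% |
| 0.5 | 0.11 | 0.54 | 7.5% |
| 1 | 0.22 | 1.08 | 17.9% |
| 2 | 0.44 | 2.17 | 54.6% |

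**Step 3: sensitivity to the quantile**

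Counting exclusion of 0 on either side, the t version gives 8.1%, 18.0% and 54.7%. The normal version, which matches the protocol's 1.8, gives 8.4%, 19.2% and 58.2%. The choice makes little difference.

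**Step 4: a benchmark from the protocol itself**

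A shift equal to the planned half-width (about 1.8 cells) makes the interval exclude 0 in 46% (t) to 50% (normal) of trials with no true effect.

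**Step 5: effect of masking on the plan's figures**

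Masking leaves n = 24 and the half-width of 1.81 unchanged. If it brought b to 0, the upper-side rate would return to 2.5%.

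**The case against.** The strongest objection is that the argument relies on silence in a document that is largely hidden at the relevant place. Slide preparation and reading would naturally be described in the visit procedures and around Table 8-1, and that text is blacked out or absent from view. A reader might infer that the protocol has no reader masking at all. The documents do not support that. What they support is that Section 6.3, the visible section for the subject, does not state it. This objection stands, and it makes the fix conditional.

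A reader might also take the open-label entry in Appendix 5 as proof that slides are read unmasked. It is not. That field classifies the trial, and an open-label trial can still have a masked laboratory reader.

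Nor can it be stated as fact that the count is a matter of judgment. The visible text does not say whether counting is manual or automated, or who does it. With manual classification, judgment is involved. With automated counting, field selection and thresholds may still leave room for it. The concern holds to the extent that a person makes any such choice.

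The shifts of 0.5, 1 and 2 cells have no source in the protocol. They show what a bias of that size would do, not that one is likely. This also stands.

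One might say that the matter belongs in the SAP. That is weaker. Coding and reading order are conduct measures that must be fixed before slides are read, and Section 6.3 names blinding as its own subject.

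**Conclusion.** The point holds in a limited, conditional form and should be acted on. In the visible text, the section that should fix masking fixes only randomization. The primary result is an uncontrolled before/after count whose expected direction is stated in advance. If reading involves any judgment and the reader can see the visit, the primary estimate is open to a shift that the planned analysis cannot tell apart from a device effect.

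The size is illustrative: 7.5%, 18% and 55% instead of 2.5% for assumed shifts of 0.5, 1 and 2 cells. It rests on n = 24, SD 4.52 read as cells, no true effect, and the added rule that the CI lies above 0.

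A reader might go on to conclude that masked reading would make the primary result unbiased. It would not. Specimens are still collected open-label, and anything that changes over the 30 to 60 days between visits stays in the within-arm contrast.

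**What to change.** Unless the redacted assay text already does so, add to Section 6.3 that:

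- slides, or their stored images, carry a code only;
- the reader is masked to participant, visit and arm;
- each participant's two slides are read together, in random order;
- the code is released only after the counts are locked.

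If the redacted text already covers this, a cross-reference from Section 6.3 is enough. Section 6.3 should also say whether counting is manual or automated, where this is not stated elsewhere.

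The cost is slide coding and a code list. Screening slides or images must also be held until the Application Visit slides are ready, at least 30 to 60 days and longer if several participants are batched. Screening counts are not available in the meantime. The visible text does not say whether specimens keep that long, so the laboratory should confirm it or read from stored images. No change to the sample size, the participant procedures or the number of readers is needed.
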